## **8.4 Reporting Procedures – Notifying the IRB**

### **8.4.1 Adverse Event Reporting**

Adverse events that do not meet criteria as Serious Adverse Events or Unanticipated Problems will be reported to the IRB at the time of annual continuation review.

### **8.4.2 Serious Adverse Event Reporting**

Serious adverse events will be reported to the IRB within 72 hours.

### **8.4.3 Unanticipated Problem Reporting**

Incidents or events that meet the OHRP criteria for UPs require the creation and completion of an UP report form. It is the site investigator's responsibility to report UPs to their IRB and to the study sponsor. The UP report will include the following information:

- Protocol identifying information: protocol title and number, PI's name, and the IRB project number;
- A detailed description of the event, incident, experience, or outcome;
- An explanation of the basis for determining that the event, incident, experience, or outcome represents an UP;
- A description of any changes to the protocol or other corrective actions that have been taken or are proposed in response to the UP.

To satisfy the requirement for prompt reporting, UPs will be reported using the following timeline:

- UPs that are SAEs will be reported to the IRB and to the study sponsor within 72 hours of the investigator becoming aware of the event.
- Any other UP will be reported to the IRB and to the study sponsor within 7 business days of the investigator becoming aware of the problem.
- All UPs should be reported to appropriate institutional officials (as required by an institution's written reporting procedures), the supporting agency head (or designee), and OHRP within<insert timeline in accordance with policy> of the IR's receipt of the report of the problem from the investigator.

### **8.4.4 Reporting of Pregnancy**

Pregnancy will be reported to the IRB within 72 hours. If pregnancy is discovered before administration of the two doses of ferumoxytol injection, participation in the study will be terminated. If pregnancy is determined during the 6-month follow-up period, the subject will be requested to allow continued follow-up to determine the pregnancy outcome.

CONFIDENTIAL

This material is the property of the NYU School of Medicine and Langone Medical Center. Do not disclose or use except as authorized in writing by the study sponsor  
Interventional Template Version: 28 APR 2017

## **8.5 Reporting Procedures – Notifying the Study Sponsor**

The study clinician will complete a SAE Form within the following timelines:

- All deaths and immediately life-threatening events, whether related or unrelated, will be recorded on the SAE Form and submitted to the study sponsor within 72 hours of site awareness. See Section 1, Key Roles for contact information.
- Other SAEs regardless of relationship will be submitted to the study sponsor within 72 hours of site awareness.

All SAEs will be followed until satisfactory resolution or until the site investigator deems the event to be chronic or the adherence to be stable. Other supporting documentation of the event may be requested by the DCC/study sponsor and should be provided as soon as possible.

As a follow-up to the initial report, within the following 48 hours of awareness of the event, the investigator shall provide further information, as applicable, on the unanticipated event or the unanticipated problem in the form of a written narrative. This should include a copy of the completed Unanticipated Problem form, and any other diagnostic information that will assist the understanding of the event. Significant new information on ongoing unanticipated adverse effects shall be provided promptly to the study sponsor.

## **8.6 Study Halting Rules**

Administration of study agent will be halted when three grade 3 AEs determined to be “probably related” are observed.

It is the responsibility of the Principal Investigator to oversee the safety of the study. This safety monitoring will include careful assessment and appropriate reporting of adverse events as noted above, as well as the construction and implementation of a site data and safety-monitoring plan. The data and safety monitoring plan will include systematic review of accrual, protocol deviations, data integrity and adverse event monitoring by the PI on an ongoing basis. The PI will report a summary of the data and safety monitoring record to the IRB at the time of annual continuation application, or earlier in accord with IRB regulation in the event of Reportable New Information.

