## **2.4 Potential Risks & Benefits**

### **2.4.1 Known Potential Risks**

Ferumoxytol injection has been demonstrated to be safe and effective in the treatment of iron deficiency anemia and is FDA-approved for treatment of iron deficiency in adult patients with chronic kidney disease. The most common adverse reactions ( $\geq 2\%$ ) following the administration of Ferumoxytol injection are diarrhea, nausea, dizziness, hypotension, constipation, and peripheral edema. Fatal and serious hypersensitivity reactions including anaphylaxis have occurred in patients receiving ferumoxytol injection. In clinical studies predominantly in patients with CKD, serious hypersensitivity reactions were reported in 0.2% (3/1,726) of subjects receiving Ferumoxytol injection. Other adverse reactions potentially associated with hypersensitivity (e.g., pruritus, rash, urticaria or wheezing) were reported in 3.7% (63/1,726) of these subjects. In other trials excluding patients with Stages 4 and 5 CKD, moderate to severe hypersensitivity reactions were reported in 2.6% (26/1,014) of patients treated with ferumoxytol injection. Severe adverse reactions of clinically significant hypotension have been reported in the post-marketing experience. In clinical studies, hypotension was reported in 1.9% (33/1,726) of subjects, including three patients with serious hypotensive reactions. The following additional serious adverse reactions have been reported from the post-marketing experience with ferumoxytol injection : tachycardia/rhythm abnormalities, angioedema, ischemic myocardial events, congestive heart failure, pulse absent, and cyanosis. This safety information is derived from studies in patients with chronic kidney disease with or without dialysis requirement. The dosing and route of administration used in this study are consistent with the FDA-approved prescribing information for this drug. There is no reason to suspect that VAD patients with iron deficiency are at greater risk for adverse effects of ferumoxytol injection when compared with completed clinical trials and post-marketing experience in chronic kidney disease patients.

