## 8.2 Classification of an Adverse Event

### 8.2.1 Severity of Event

For AEs not included in the protocol defined grading system, the following guidelines will be used to describe severity.

- **Mild** – Events require minimal or no treatment and do not interfere with the participant's daily activities.
- **Moderate** – Events result in a low level of inconvenience or concern with the therapeutic measures. Moderate events may cause some interference with functioning.
- **Severe** – Events interrupt a participant's usual daily activity and may require systemic drug therapy or other treatment. Severe events are usually potentially life-threatening or incapacitating.

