### 8.2.2 Relationship to Study Agent

The clinician's assessment of an AE's relationship to study agent (drug, biologic, device) is part of the documentation process, but it is not a factor in determining what is or is not reported in the study. If there is any doubt as to whether a clinical observation is an AE, the event will be reported.

For all collected AEs, the clinician who examines and evaluates the participant will determine the AE's causality based on temporal relationship and his/her clinical judgment. The degree of certainty about causality will be graded using the categories below.

- **Definitely Related** – There is clear evidence to suggest a causal relationship, and other possible contributing factors can be ruled out. The clinical event, including an abnormal laboratory test result, occurs in a plausible time relationship to drug administration and cannot be explained by concurrent disease or other drugs or chemicals. The response to withdrawal of the drug (dechallenge) should be clinically plausible. The event must be pharmacologically or phenomenologically definitive, with use of a satisfactory rechallenge procedure if necessary.
- **Probably Related** – There is evidence to suggest a causal relationship, and the influence of other factors is unlikely. The clinical event, including an abnormal laboratory test result, occurs within a reasonable time after administration of the drug, is unlikely to be attributed to concurrent disease or other drugs or chemicals, and follows a clinically reasonable response on withdrawal (dechallenge). Rechallenge information is not required to fulfill this definition.
- **Possibly Related** – There is some evidence to suggest a causal relationship (e.g., the event occurred within a reasonable time after administration of the trial medication). However, other factors may have contributed to the event (e.g., the participant's clinical condition,

CONFIDENTIAL

other concomitant events). Although an AE may rate only as “possibly related” soon after discovery, it can be flagged as requiring more information and later be upgraded to “probably related” or “definitely related,” as appropriate.

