## 8.3 Time Period and Frequency for Event Assessment and Follow-Up

The occurrence of an AE or SAE may come to the attention of study personnel during study visits and interviews of a study participant presenting for medical care, or upon review by a study monitor. All AEs including local and systemic reactions not meeting the criteria for SAEs will be captured on the appropriate RF. Information to be collected includes event description, time of onset, clinician’s assessment of severity, relationship to study product (assessed only by those with the training and authority to make a diagnosis), and time of resolution/stabilization of the event. All AEs occurring while on study must be documented appropriately regardless of relationship. All AEs will be followed to adequate resolution.

Any medical condition that is present at the time that the participant is screened will be considered as baseline and not reported as an AE. However, if the study participant’s condition deteriorates at any time during the study, it will be recorded as an AE. UPs will be recorded in the data collection system throughout the study.

Changes in the severity of an AE will be documented to allow an assessment of the duration of the event at each level of severity to be performed. AEs characterized as intermittent require documentation of onset and duration of each episode.

The PI will record all reportable events with start dates occurring any time after informed consent is obtained until 7 (for non-serious AEs) or 30 days (for SAEs) after the last day of study participation. At each study visit, the investigator will inquire about the occurrence of AE/SAEs since the last visit. Events will be followed for outcome information until resolution or stabilization.

All unresolved adverse events should be followed by the investigator until the events are resolved, the subject is lost to follow-up, or the adverse event is otherwise explained. At the last scheduled visit, the investigator should instruct each subject to report any subsequent event(s) that the subject, or the subject’s personal physician, believes might reasonably be related to participation in this study. The investigator should notify the study sponsor of any death or adverse event occurring at any time after a subject has discontinued or terminated study participation that may

CONFIDENTIAL

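### The only numeric halting rule counts AEs rated Probably Related and, as worded, leaves out those rated Definitely Related

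*Combined protocol and SAP*

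**What the plan says.** Section 8.6 (Study Halting Rules) contains the only study-level stopping criterion with a number in these documents: "Administration of study agent will be halted when three grade 3 AEs determined to be" probably related. It names that one causality category, with no qualifier such as at least or or higher.

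Section 8.2.2 (Relationship to Study Agent) sets the causality scale: "The degree of certainty about causality will be graded using the categories below". There are five categories, from Definitely Related down to Not Related. The top one is defined by "There is clear evidence to suggest a causal relationship, and other possible contributing factors can be ruled out". Probably Related comes next, with a weaker requirement: other factors need only be unlikely. For an event first rated possibly related, the section says "it can be flagged as requiring more information and later be upgraded to" either of the two higher categories, which it names as alternatives.

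The other relevant provisions carry no count. Section 5.7.1 lets an investigator stop an individual participant. Section 5.8 says the study may be suspended or terminated, for example for unacceptable risk. Sections 8.4 and 8.5 deal with reporting, with SAEs going to the IRB and the sponsor within 72 hours.

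**The concern.** A halting rule based on causality should become more likely to fire as the evidence against the drug strengthens. As worded, this one does the reverse at the top of the scale. An event moved from Probably to Definitely leaves the count, so better evidence of causation makes a mandatory halt less likely.

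What is at stake is participant safety, not inference. No endpoint, analysis or sample size depends on the rule. It matters because section 2.3 says there are no previous data on the safety of this regimen in the VAD population, and because section 2.4.1 records fatal and serious hypersensitivity reactions with the drug. Section 2.4.1 also lists pre-specified criteria for stopping the study among the protections for participants, and 8.6 is the only one with a number. Under 8.1 the PI is also the medical monitor, and the documents describe no independent committee that would interpret the rule.

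**Working it through.** **Step 1. The rule against the scale.** The plan gives no probability or operating characteristic for the rule, so there is no figure to reproduce. The check is a count, where the worded rule counts Probably only and the corrected rule counts Probably plus Definitely.

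| Grade 3 AEs observed | Worded count | Corrected count | Worded halt | Corrected halt |
|---|---|---|---|---|
| 3 Probably | 3 | 3 | yes | yes |
| 3 Definitely | 0 | 3 | no | yes |
| 2 Probably + k Definitely (k ≥ 1) | 2 | 2 + k | no | yes |

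The defect follows from this alone. The remaining steps only size it.

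**Step 2. Inputs for the size.**
- n = 20 participants (section 5.6); halt at 3 (section 8.6).
- Per-patient rates p from section 2.4.1:
  - "serious hypersensitivity reactions were reported in 0.2% (3/1,726) of subjects receiving Ferumoxytol injection", so p = 3/1,726 = 0.00174.
  - Adding the serious cases in "hypotension was reported in 1.9% (33/1,726) of subjects, including three patients with serious hypotensive reactions", and assuming no overlap, p = 6/1,726 = 0.00348.
  - Moderate-to-severe hypersensitivity in other trials, p = 26/1,014 = 0.02564. This overstates severe events because it includes moderate ones.
- d, the share of qualifying events rated Definitely. The documents do not give it, so 10%, 25% and 50% are assumptions.
- Simplifications: at most one qualifying event per patient, and independent ratings.

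**Step 3. Chance that the corrected rule fires.** P(X ≥ 3) with X ~ Bin(20, p) is 1 − Σ C(20,k) p^k (1−p)^(20−k), summed over k = 0, 1, 2. For p = 0.02564 the three terms are 0.59481 + 0.31306 + 0.07826 = 0.98613, which leaves 0.0139. The other two rates give 5.9 × 10⁻⁶ and 4.6 × 10⁻⁵.

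**Step 4. Chance that the wordings differ.** The worded rule sees the rate p(1 − d). Whenever it fires, the corrected rule fires too, so the difference is P(Bin(20, p) ≥ 3) − P(Bin(20, p(1−d)) ≥ 3).

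| p | Corrected rule fires | Differ, d = 10% | Differ, d = 25% | Differ, d = 50% |
|---|---|---|---|---|
| 3/1,726 | 0.0006% | 0.00016% | 0.0003% | 0.0005% |
| 6/1,726 | 0.005% | 0.0012% | 0.003% | 0.004% |
| 26/1,014 | 1.4% | 0.34% | 0.75% | 1.2% |

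The last cell is 1.386% − 0.204% = 1.18%. Even if every event were rated Definitely, the difference could not exceed the second column, so 1.4% at most.

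**Step 5. Beyond the documented rates.** Section 8.6 counts all grade 3 related AEs, not just hypersensitivity and hypotension, and the documents give no rate for that whole set. For illustration only, with d = 50%: at an assumed 5% per patient the corrected rule fires with probability 7.5% and the worded one 1.3%, a difference of 6.3 points before rounding. At an assumed 10% the figures are 32.3% and 7.5%, a difference of 24.8 points.

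**The case against.** The strongest reply is that this is copy-editing. The causality categories are ordered by certainty, a safety threshold on an ordered scale is normally read as a floor, and a PI reviewing AEs on an ongoing basis would very likely count Definitely events. Three severe reactions definitely caused by the drug would plainly meet the unacceptable-risk ground in 5.8. All of that stands as a reason to expect little harm. It does not repair the text. Section 8.2.2 treats the two categories as alternatives, and 5.8 permits a stop where 8.6 requires one.

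Three stronger readings are tempting, and the documents support none of them.

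- A reader might infer that dosing would continue unchecked after severe, definitely related reactions. The discretionary stops and the 72-hour SAE reporting contradict that. Section 8.6 also calls for a site data and safety-monitoring plan that is not in these documents and may or may not restate the trigger.
- A reader might infer a large failure rate by starting from exactly three qualifying events: 1 − (1 − d)³ is 27%, 58% and 88% at d = 10%, 25% and 50%. Those figures rest on an assumed d and on the rare event having already occurred, and a later Probably event could still trigger the halt. Low d is also the more plausible end, because a Definitely rating requires other causes to be ruled out.
- A reader might infer that grade 3 simply means Severe, given "Severe events are usually potentially life-threatening or incapacitating", and rewrite it so. Section 8.2.1 applies Mild, Moderate and Severe to AEs outside a protocol-defined grading system, and the documents do not show such a system. The substitution could change which events count.

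**Conclusion.** The concern holds: section 8.6 is wrong as written, because its mandatory trigger excludes the category with the strongest evidence of causation. It is minor. At the rates in section 2.4.1 the two wordings differ with probability of about 1.2% or less. This assumes 20 patients, at most one qualifying event each, independent ratings and no more than half of the events rated Definitely. The figure covers hypersensitivity and hypotension only and is not an upper bound for all severe related AEs, for which the documents give no rate. The conclusion that the wording is defective rests on the text of 8.6 and 8.2.2 and on none of these assumptions.

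**What to change.** In the first sentence of section 8.6, change the causality term to *probably or definitely related*. Keep the count of three, and leave grade 3 as it stands.

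The cost is one phrase and IRB approval of the amendment. No new data are needed, because section 8.3 already requires the clinician's "assessment of severity, relationship to study product (assessed only by those with the training and authority to make a diagnosis") to be recorded. The chance of halting rises by the differences shown in the working, and only in cases where the evidence against the drug is at least as strong as the present rule requires.

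Separately, the sponsor should confirm what grade 3 means against the scale in 8.2.1, and whether higher grades, if any exist, also count. That question is not part of this change.

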# **9 Statistical Considerations**

## **9.1 Statistical and Analytical Plans (SAP)**

The statistical analysis plan is summarized in the following sections.

## **9.2 Statistical Hypotheses**

Primary Feasibility Objective: The null hypothesis for the primary feasibility objective is that 75% of the subjects will successfully complete ferumoxytol injection treatment as per study protocol.

CONFIDENTIAL

This material is the property of the NYU School of Medicine and Langone Medical Center. Do not disclose or use except as authorized in writing by the study sponsor  
Interventional Template Version: 28 APR 2017

There are no hypotheses to be tested for the primary safety objective and exploratory secondary objectives. Descriptive statistics will be used to analyze these data. The purpose of the analyses is to obtain estimates of the study treatment risk in the study population, and the magnitude and variance of change in the exploratory endpoints in the study population. These pilot data will be useful for planning of future clinical trials.

### **9.3 Analysis Datasets**

Feasibility analysis dataset. Intention to treat (ITT) will be defined as all patients who provide consent and are eligible to receive study treatment. The ITT data set will be used for the primary feasibility endpoint.

Safety objective and exploratory objectives analysis dataset. All eligible subjects who received any study drug, and for whom post-dose data are available, will be included in the safety and exploratory objectives analysis set.

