### 5.2 Exclusion Criteria

An individual who meets any of the following criteria will be excluded from participation in this study:

- Known hypersensitivity to Ferumoxytol injection or other intravenous iron preparation

CONFIDENTIAL

This material is the property of the NYU School of Medicine and Langone Medical Center. Do not disclose or use except as authorized in writing by the study sponsor  
Interventional Template Version: 28 APR 2017

- History of anaphylaxis
- Treatment with erythropoiesis stimulating agent or intravenous iron in last 3 months
- Renal failure on hemodialysis
- Respiratory failure on mechanical ventilation
- Disabling Stroke
- Ventricular assist device thrombosis
- Evidence of active gastrointestinal bleeding or other active blood loss
- Hospitalization <30 days
- Pregnant or breastfeeding women

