### **5.7 Participant Withdrawal or Termination**

#### **5.7.1 Reasons for Withdrawal or Termination**

CONFIDENTIAL

This material is the property of the NYU School of Medicine and Langone Medical Center. Do not disclose or use except as authorized in writing by the study sponsor  
Interventional Template Version: 28 APR 2017

Participants are free to withdraw from participation in the study at any time upon request. An investigator may terminate participation in the study if:

- Any clinical adverse event (AE), laboratory abnormality, or other medical condition or situation occurs such that continued participation in the study would not be in the best interest of the participant
- The participant meets an exclusion criterion (either newly developed or not previously recognized) that precludes further study participation
- The participant is not able to return for the second dose of ferumoxytol within 15 days of the first dose.

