### **5.7.2 Handling of Participant Withdrawals or Termination**

Withdrawn or terminated participants will be followed for extraction of clinical data from the medical record for 6 months with participant permission. Since the primary outcome is feasibility, there will be no replacement of withdrawn subjects.

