# **7 Study Procedures and Schedule**

## **7.1 Study Procedures/Evaluations**

### **7.1.1 Study Specific Procedures**

Study visits (See Attached Study Schematic Figure and Schedule of Assessments Table): The study will require 3 visits over approximately 2 weeks for each subject.

- Visit 1: Informed consent and screening\*
- Visit 2: First dose of ferumoxytol injection Study Drug\*
- Visit 3: Second dose of ferumoxytol injection Study Drug

\*Visits 1 and 2 may occur on the same day.

Screening procedures. After the informed consent form is signed, chart review and patient interview will be performed to determine eligibility. Screening will include subject interview and chart review to determine eligibility. Clinical information on co-morbid conditions, VAD settings, and concomitant medications will be collected. Vital signs in the seated position and a brief cardiovascular exam will be recorded. Women of childbearing potential will undergo urine or blood pregnancy testing.

Study Drug Administration: Ferumoxytol injection will be administered to eligible subjects according to FDA-approved prescribing information. Prior to administration, interim history, concomitant medications, VAD settings, vital signs and a cardiovascular exam will be recorded. Two doses of ferumoxytol injection will be administered: an initial 510 mg dose followed by a second 510 mg dose 3 to 8 days later, each dose given as an intravenous infusion in 50-200 mL 0.9% Sodium Chloride Injection, USP or 5% Dextrose Injection, USP while the subject is in a reclined or semi-reclined position. Subjects will be observed for signs or symptoms of hypersensitivity reactions (including monitoring of blood pressure and pulse rate) during and for at least 30 minutes after ferumoxytol injection administration. The dose, date and time of infusion, duration of infusion, and treatment-related adverse effects (diarrhea, nausea, dizziness, hypotension, hypersensitivity) will be recorded.

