#### **9.4.4 Safety Analyses**

Descriptive analysis techniques will be used to characterize clinical characteristics of the study participants, and incidence of adverse events and change in secondary exploratory outcomes. Center and variability of continuous variables will be presented as means (SD) when they follow a normal distribution and as medians and interquartile range otherwise. Log transformation will be applied on variables with skewed distribution

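### Does restricting the safety set to eligible subjects drop a dosed subject whose exclusion criterion is recognized only later?

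*Combined protocol and SAP*

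**What the plan says.** Section 9.3 gives the only definition of the safety population: "All eligible subjects who received any study drug, and for whom post-dose data are available, will be included in the safety" and exploratory set. The sentence before it defines the intention-to-treat set for the feasibility endpoint as "all patients who provide consent and are eligible to receive study treatment". Neither sentence dates the eligibility decision.

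Section 9.4.4 (Safety Analyses) names no population; it says only that "Descriptive analysis techniques will be used to characterize clinical characteristics of the study participants, and incidence of adverse events" and of change in the exploratory outcomes. Section 9.2 states the aim: "The purpose of the analyses is to obtain estimates of the study treatment risk in the study population", with no safety hypothesis to be tested.

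On withdrawal, section 5.7.1 allows an investigator to end participation if "The participant meets an exclusion criterion (either newly developed or not previously recognized) that precludes further study participation". Section 5.7.2 then provides: "Withdrawn or terminated participants will be followed for extraction of clinical data from the medical record for 6 months with participant permission". It also rules out replacing withdrawn subjects, because the primary outcome is feasibility.

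**The concern.** A safety population is normally everyone exposed to the drug. Here an extra word, *eligible*, stands in front of exposure. Section 5.2 bars from the study anyone who meets an exclusion criterion, so in hindsight a subject with a missed criterion was never eligible. A literal reader could delete that subject, and any reaction, from the numerator and denominator of the safety endpoint.

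The case is possible. Screening eligibility rests on history: after consent, "chart review and patient interview will be performed to determine eligibility". The first dose may follow on the same day, and the criteria are checked again at Visit 3, when one dose has already been given (section 7.3.3). A past event such as "History of anaphylaxis" might surface only because a reaction led someone to retake the history. Late-found ineligibility would then be linked to having an event, and the incidence would be biased downward in a trial of 20 subjects.

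**Working it through.** **Step 1: how the protocol uses the word.**

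- Section 7.1.1: eligibility is determined by chart review and interview after consent, and ferumoxytol is then given to eligible subjects. Eligibility comes before the dose.
- Section 7.3.1: a participant who is eligible for the drug may have the first administration on the screening day. Again this is a pre-dose decision.
- Section 9.3, intention-to-treat sentence: eligibility is eligibility to receive treatment, which looks forward to dosing.

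Read consistently, eligible subjects who received any drug are those who were cleared and then dosed.

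**Step 2: what the withdrawal sections do.** Section 5.7.1 treats newly developed and previously unrecognized criteria alike, as grounds on which participation *may* end. A newly developed criterion cannot make someone ineligible in the past, so the clause concerns continuing, not entry status. Section 5.7.2 keeps extracting data from these participants, with permission, and does not replace them. Section 5.6 expects 20 enrolled to yield 20 evaluable, with no allowance for later removals. None of this takes anyone out of an analysis set.

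**Step 3: can eligibility be re-judged after dosing?** Section 7.3.3 repeats the criteria check at Visit 3. One criterion in section 5.2 is intravenous iron in the last 3 months. Applied literally at Visit 3, every subject given the first dose would meet it. Eligibility for analysis therefore cannot mean the criteria applied afresh after dosing. This rules out only that variant; a retrospective view of pre-dose status still has to be answered by steps 1 and 2.

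**Step 4: size under the hindsight reading.** The plan gives no figure on this point. Assumptions: 20 dosed (all those enrolled under section 5.6), one left out, and k = 1, 2 or 3 subjects with a treatment-related event.

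- All dosed: k/20.
- The subject left out had an event: (k − 1)/19.
- The subject left out had none: k/19.

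| k | All dosed | Left out, had event | Shift (points) | Left out, no event | Shift (points) |
|---|---|---|---|---|---|
| 1 | 5.0% | 0.0% | −5.0 | 5.3% | +0.3 |
| 2 | 10.0% | 5.3% | −4.7 | 10.5% | +0.5 |
| 3 | 15.0% | 10.5% | −4.5 | 15.8% | +0.8 |

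If the late finding is unrelated to events, the subject left out had an event with probability k/20. The expected incidence is

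(k/20)(k − 1)/19 + (1 − k/20)k/19 = k(k − 1 + 20 − k)/380 = 19k/380 = k/20,

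so the mean shift is exactly zero.

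If a subject with an event is m times as likely to be the one found ineligible, then p = mk/(mk + 20 − k) and the expected incidence is (k − p)/19. For k = 1 and m = 2, p = 2/21 = 0.095 and (1 − 0.095)/19 = 4.76%, a shift of −0.24 points. The full set of mean shifts, in points:

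| k | m = 2 | m = 5 | m = 10 |
|---|---|---|---|
| 1 | −0.24 | −0.83 | −1.55 |
| 2 | −0.43 | −1.35 | −2.24 |
| 3 | −0.58 | −1.68 | −2.57 |

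**Step 5: against sampling error.** The exact (Clopper-Pearson) 95% interval for 3/20 runs from 3.2% to 37.9%, a width of 34.7 points, against a largest mean shift of 2.57. For 1/20 it is 0.1% to 24.9%; for 0/19 it is 0% to 17.6%.

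**The case for a change.** The best case for a change is that the rule is unwritten and writing it is nearly free. Section 5.2 does support a hindsight reading, so two analysts could report different denominators, and in an open-label study the choice might be made after the events are known. With 20 subjects and no replacement, one person counts: 1/20 reported as 0/19 turns one treatment-related event into none. The safety estimate is also meant to inform future trials.

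Part of this stands. The text does not state the rule, and including everyone exposed is the usual convention. But harm requires several things together: a hindsight reading that the documents never state, a criterion missed at screening and at the Visit 2 check, and a link between that finding and an event. The link is also narrower than it looks. Of the two allergy criteria, one concerns *known* hypersensitivity to intravenous iron; if it was unknown at entry, the criterion was arguably not met. The argument then rests mainly on a missed history of anaphylaxis, in patients followed regularly by a dedicated team (section 5.4).

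The condition that post-dose data be available is no reason for a change either. Subjects are observed during each infusion and for at least 30 minutes afterwards (section 7.1.1), so it should rarely bind for safety.

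**Conclusion.** This is a missing detail that an analyst would fill sensibly: eligibility is what was judged before the first dose, and a dosed subject stays in the safety set whatever is found later. A sentence saying so would do no harm, but it would not alter the analysis that the plan most naturally describes, so no change is called for.

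No bias is demonstrated. The mean effect is zero without an assumed link to events and at most 2.6 points with a tenfold link. The worst single case is 5.0 points. Those sizes rest entirely on assumed counts and multipliers and arise only under the hindsight reading. Adverse event recording and reporting (sections 8.3, 8.4 and 8.5) and the halting rule (section 8.6) apply whatever the analysis set.
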